4.2 SCIENTIFIC RATIONALE FOR STUDY DESIGN

Although this exploratory trial is not designed with statistical power to test the efficacy of OA CARE, we have included a UC group (rather than conducting a single-group study) for several reasons. First, this provides an opportunity to assess acceptability of randomization to a UC group, from the patient perspective. Second, we will be able to evaluate follow-up rates for both groups, which will inform potential adaptations and sample size estimation for a larger trial. Third, this will provide a better preliminary assessment of the efficacy of OA CARE (Aim 2) than a single group pre-post trial, since improvement is consistently observed in control groups within OA trials ^{22,29,31,38}. We have specifically selected a UC control group (versus an attention control condition) because our ultimate goal is to test how well OA CARE performs relative to the typical care patients receive for OA. Assessments for this trial will be conducted at baseline, 6-months (corresponding to the beginning of the second phase of OA CARE), and 12-months (intervention completion).

4.3 JUSTIFICATION FOR INTERVENTION

This research addresses a clear need to improve care for patients with OA through an evidence-based, comprehensive and sustainable care model. This project lays the groundwork for an implementation-focused RCT that will collect rigorous cost data to inform payment models. Involvement of key stakeholders, as well as integration with national organizations including the YMCA and OAAA, will lead to a generalizable approach and strategies for widespread implementation in U.S. healthcare systems.

4.4 END-OF-STUDY DEFINITION

A participant is considered to have completed the study if he or she has completed 12-month follow-up assessment.

5 STUDY POPULATION

5.1 INCLUSION CRITERIA

Participants for this trial will be patients with a clinician diagnosis of knee or hip OA, self-reported knee or hip pain of ≥ 3 (scale of 0-10) on most days of the week, body mass index (BMI) $\geq 27 \text{ kgm}^2$, and not currently meeting physical activity recommendations ³⁹. We will base study inclusion on a clinician diagnosis of hip or

knee OA, rather than obtaining new radiographs, because OA CARE is designed for providers to initiate at any point in the course of care (not necessarily directly following a diagnosis or new imaging). The rationale for BMI and physical activity criteria is that patients with higher BMI and who are inactive are at greater risk for OA progression and worse outcomes, and weight management and exercise are key components of OA CARE^{42,43}. We chose a minimum BMI of 27 kgm² because of the association with earlier mortality and the precedence of this threshold in other OA trials^{11,32,44}.

5.2 EXCLUSION CRITERIA

Exclusion Criteria and Sources of Information		
Criterion	EMR	Phone Screening
No internet access and a device (computer, tablet, smartphone) to access the virtual weight loss intervention		X
Pain in chest when performing physical activity		X
Pain in chest when not performing physical activity		X
No documented diagnosis of knee or hip OA	X	X
No lower extremity surgery in the past 6 months	X	X
Significant cognitive impairment	X	X
Psychosis	X	X
Uncontrolled Substance abuse disorder	X	X
Severe hearing or visual impairment	X	X
Serious/terminal illness as indicated by referral to hospice or palliative care	X	X
Hospitalization for cardiovascular event in last 6 months	X	X
History of ventricular tachycardia	X	X
Unstable chronic obstructive pulmonary disease (2 hospitalizations within the previous 6 months and/or on oxygen)	X	X
Stroke with moderate to severe aphasia	X	X
Recent history (last 6 months) of three or more falls		X
Planning total joint replacement in next 6 months		X
Any other health conditions determined by the study team to be contraindications to a home exercise program or weight loss.	X	X
Current participation in other study related to knee or hip osteoarthritis, weight loss or physical activity		X
Unable to speak English	X	X
Pregnant or planning to become pregnant	X	X

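### The recent-surgery row in the exclusion table (5.2) runs opposite to the table's heading and to its comparable rows

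*Combined protocol and SAP*

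**What the plan says.** The table in 5.2 is headed as exclusion criteria with their sources of information. It marks each row for checking in the electronic record, by phone, or both. The row at issue, "No lower extremity surgery in the past 6 months", is marked for both.

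Two other rows begin with a negative: one on internet access and a device, and "No documented diagnosis of knee or hip OA". Four other rows carry a six-month window:

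- "Hospitalization for cardiovascular event in last 6 months"
- the unstable lung disease row, defined by "2 hospitalizations within the previous 6 months and/or on oxygen"
- "Recent history (last 6 months) of three or more falls"
- "Planning total joint replacement in next 6 months"

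A catch-all row covers "Any other health conditions determined by the study team to be contraindications to a home exercise program or weight loss".

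The inclusion criteria in 5.1 begin "Participants for this trial will be patients with a clinician diagnosis of knee or hip OA" and go on to pain, BMI and activity level. They do not mention surgery.

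**The concern.** In an exclusion list, a true statement about the patient removes that patient. The surgery row is worded as a condition to be satisfied, so its literal effect is to remove patients with no recent leg surgery. 5.1 asks for nothing about surgery, so the literal row would turn away patients who fit 5.1 merely for not having had an operation.

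Three things depend on the row.

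- **Entry to the trial.** Under 5.5 staff screen the record for exclusions, and under 10.1.1.2 passing the record and telephone criteria is the gate to the baseline visit.
- **Compliance after enrolment.** 10.1.10 counts any departure from the protocol as a deviation. If staff apply the opposite meaning, every participant enrolled without recent surgery meets a written exclusion. 7.2 also lists meeting a previously unrecognised exclusion that rules out further participation as a ground for discontinuing a participant.
- **A reported result.** Feasibility is Aim 1. Sections 8.1 and 9.4 both report the proportion of patients who are eligible, so literal or mixed use of the row would change that figure.

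**Working it through.** The plan gives no figure to reproduce. The check is a reading of all 20 rows under the table's heading, followed by a search for any text that settles the surgery row.

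**1. Count of rows.** There are 20 criterion rows. Fourteen, including the surgery row, are marked for both record and phone, and 6 for phone only (14 + 6 = 20). Nineteen work as a reason to exclude if true. The surgery row does not.

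**2. Is there a convention of negative wording?** Three rows begin with a negative:

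| Row | Literal effect | Support elsewhere |
|---|---|---|
| Internet access and device | Absence excludes | 6.1 treats such a patient as ineligible for that reason |
| OA diagnosis | Absence excludes | 5.1 requires a clinician diagnosis |
| Lower-extremity surgery | Absence excludes | None |

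The first two are correct exclusions as written. The table is therefore not a list of conditions to be met, and the surgery row cannot be explained that way.

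**3. Comparison with the other time-windowed rows.** Five rows carry a six-month window:

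| Row | Excludes on |
|---|---|
| Cardiovascular hospitalization | Presence |
| Unstable lung disease | Presence |
| Three or more falls | Presence |
| Planned joint replacement | Presence |
| Lower-extremity surgery | Absence |

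**4. Is it corrected elsewhere?** 5.1 is silent on surgery. No other section states a rule on recent leg surgery, and the amendment history in 10.4 lists no change to 5.2. The row is intact with both of its marks, so this is not damage from text extraction.

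**5. Possible effect on the eligibility proportion.** Define:

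- q = share of screened patients who pass all other criteria
- p = share of those patients with recent leg surgery
- f = share of screens that use the literal reading

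Assume that the remaining screens (1 − f) use the opposite reading, and that which reading is used is unrelated to the patient. Then:

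- Eligible proportion = q[(1 − f)(1 − p) + fp]
- With f = 0 this is q(1 − p)
- Difference = q(1 − p) − q[(1 − f)(1 − p) + fp] = qf(1 − 2p)

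The documents give none of q, p or f, so no number follows. The range is still informative. With f = 0 the difference is 0. With f = 1 it is q(1 − 2p), which approaches the whole of q as p approaches 0.

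**The case against.** The strongest reply is that nobody would apply the row literally. The neighbouring rows make the anomaly easy to see, and a screen that admitted only patients with recent leg surgery would halt recruitment at once. Sustained literal use is implausible, and the realistic risk is occasional ambiguity. The phone script, the screening form and the Manual of Procedures are not among the documents, and any of them may state the rule clearly. The quantity at risk is a descriptive proportion with no hypothesis attached, and no distortion of it has been shown. The point about deviations is formal, because it follows only from a reading that was probably not intended.

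Much of this stands as a limit on consequences. The row is most likely a slip, and nothing is known about how it was applied. The rescreening bar in 5.4 should also carry no weight here: that section defines screen failures among people who have consented, whereas this row is applied before consent. What 5.4 does show is that meeting an exclusion criterion means not meeting the criteria for participation.

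The reply does not repair the text. The approved rule says the reverse of what everyone presumes, and unseen working documents cannot correct it. The catch-all row does not either, since it could exclude patients with recent surgery only at the study team's discretion.

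**Conclusion.** The inconsistency is real and should be fixed. One of 20 rows conflicts with the table heading. It also differs from all four of the other six-month rows, and the two other negatively worded rows do not excuse it.

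The wording error rests on the text alone and needs no assumption. Any effect on the reported eligibility proportion is possible but not shown: it depends on how screeners read the row and on two shares that the documents do not give, and it is zero if the literal reading was never used. The sample size and power statement in 9.2 and the WOMAC model in 9.4 are untouched.

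**What to change.** The study team should state which rule on recent lower-extremity surgery it intends and reword the row so that it agrees with the table heading and the other rows. This review does not say what that rule should be.

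The record screen and the phone script should then be made to match. The screening log should be checked for patients classified under the other reading, and the eligibility count corrected if any are found.

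The cost is a one-row wording amendment and a check of the form, script and log. Nothing in the analysis or sample size changes.

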5.3 LIFESTYLE CONSIDERATIONS

N/A

5.4 SCREEN FAILURES

Screen failures are defined as participants who consent to participate in this study but are not subsequently assigned to the study intervention or entered in the study. Individuals who do not meet the criteria for participation in this trial (screen failure) because of meeting one or more exclusion criteria (e.g., development of an exclusionary health condition) will not be rescreened.

5.5. STRATEGIES FOR RECRUITMENT AND RETENTION

We will recruit patients from UNC Health. In particular, we will partner with the UNC Internal Medicine Clinic and UNC Family Medicine, which serves high proportions of patients who are African American and non-white Hispanic, as well as uninsured patients. This is important because of disparities in OA among these demographic groups⁴⁵, and our aim for *OA CARE* to particularly reach the most vulnerable patients. Our team has a strong track record of recruiting African American and non-White Hispanic patients^{28,31,46}. Our main recruitment method will mirror the process by which we envision *OA CARE* will ultimately function in clinical settings. Specifically, PCPs will be asked to refer patients to *OA CARE*. This may occur via the EHR or another UNC approved method of transferring PHI. A study team member will then screen the EHR for potential exclusion criteria and contact the patient to assess interest and administer a brief screening questionnaire. If needed, we will also identify potential participants via an EHR data pull, then send introductory letters and follow up with a screening phone call. However, a key goal for this exploratory study is to develop procedures to maximize provider referrals, as this will be critical for downstream implementation. All eligible patients will be asked to attend a baseline visit that will involve completion of consent, baseline assessments and receipt of an accelerometer. Following return of the accelerometer, participants will be informed of their randomization assignment via telephone. A participant will be considered enrolled once they have consented and been randomized.

To facilitate completion of recruitment calls, as well as baseline and follow-up assessment calls, we will call participants on different times of day and different days, across multiple weeks. We have used this strategy successfully in prior studies to reach participants at times convenient to them.

6.0 STUDY INTERVENTIONS**6.1 STUDY INTERVENTION ADMINISTRATION*****OA CARE* Intervention**

OA Clinic-Community CARE Model (OA CARE)

Protocol #22-0865

Overview. For patients, OA CARE includes evidence-based behavioral weight management and exercise interventions, as well as tailored referrals to physical therapy, psychological interventions, additional weight / nutrition-related services and sleep-related services based on patient-specific needs and in coordination with the PCP (Figure 2). These referrals will be based on screening questions administered six months after initiating weight management and exercise interventions; the rationale for this timing is that it allows us to evaluate which additional services patients may need after engaging in “first line” therapies for a meaningful period of time ^{4,8,10}. PCPs of patients enrolled in OA CARE will be given a video-based summary of ACR treatment guidelines ¹⁰, collaborate on patient referrals, and receive brief progress reports on their enrolled patients. An OA CARE Navigator will facilitate all activities within the care pathway, including scheduling patients for weight management and exercise classes (in collaboration with the YMCA), conducting 6-month screening questions, coordinating referrals with

PCPs, preparing patient progress reports for PCPs, and serving as a point person for both patient and PCPs. Importantly for implementation, the OA CARE Navigator role does not require clinical or other specialized expertise, so in clinical settings this role could be performed by a variety of personnel (e.g., chronic care managers, nurses, schedulers).

Weight Loss & Exercise Interventions. Evidence-based weight loss and exercise programs will be delivered by the Triangle YMCA, within the structure of the Medical Membership. (All services provided to study participants by the YMCA will be their standard programming; they will note be delivering a study-specific intervention.) This membership provides access to multiple group exercise programs, exercise facilities, and a health coach who assists members with meeting health goals and selecting appropriate programs and classes. All patients in OA CARE will begin with participation in the YMCA’s Weight Loss Program (Program). This program involves 12 weekly sessions that include goal-setting, food and activity tracking, introduction to physical activity offerings, and weigh-ins. This Program is based on best practices from evidence-based behavioral weight loss programs. Participants may repeat the program following the first 12-week session if they have not met weight loss goals and / or would like continued structure and support for these behavior changes. The Triangle YMCA will deliver the Weight Loss Program to OA CARE members in groups of approximately 10; this will provide cohesion for OA CARE participants. In the beginning of the study, the Program will be delivered virtually (e.g. video conferencing platform) for feasibility reasons (e.g., potential for study participants to reside in different geographic locations that would make travel to a central location challenging). However, the Program may be offered in-person in the future. During the screening call, we will assess whether the patient has internet access and a device (computer, tablet, smartphone) on which they can access the Program. If the patient screens ineligible for this reason, we will ask the patient if they would like to be contacted, if the Program is offered in-person at a future date. If we do offer the Program in person, this will no longer be considered an exclusion criterion. The YMCA offers many exercise programs and classes appropriate for individuals with OA. A YMCA health coach will assist participants with selecting an exercise program (including appropriateness based on their pain and functional limitations) and continuing to engage with exercise-based therapies throughout their 12-month involvement in OA CARE. The UNC study team will also give participants instructions regarding how to access a free Walk With Ease workbook (through the OAAA’s online portal) and take advantage of other tools available through this program.

Version 4.0

[figure not shown]

Figure 2. OA CARE Intervention

Additional Tailored Services. After 6-months, we will administer a series of questionnaires to assess patients' needs for and interest in additional interventions included in OA treatment guidelines (Table 1) ^{10,20}. Our multidisciplinary study team, which includes individuals with deep expertise in OA treatment and guidelines, has developed algorithms to guide these referrals. Patients will be given information on the types of interventions shown in Table 1 (via mail or email), and the OA CARE Navigator will engage patients in a shared decision-making process (via phone) regarding additional referrals, with a focus on interventions for which they meet criteria shown in Table 1. However, the OA CARE Navigator will facilitate referrals and recommendations for any services of interest to patients, regardless of criteria shown in the table. Any referrals for clinically-based services (e.g., physical therapy, sleep testing) will be coordinated with the PCP. Table 1 also shows examples of interventions and resources within each category, ranging from free, publicly available programs to individual clinical services; some services will be relevant regardless of geographic location and some will be customized based on local resources, as we have done previously ³³. The OA CARE Navigator will also call participants about a month later to follow up on any questions they may have regarding resources or referrals. The OA CARE Navigator may also conduct additional calls with a participant if needed to coordinate connection with resources or referrals.

Table 1. Criteria and Examples of Additional Tailored Services

Type of Service	Criteria	Example Interventions & Resources
Psychological Interventions	Subgroups for Targeted Treatment (STarT Back) Tool ⁴⁷⁻⁴⁹ : 4 or more psychosocial risk factors (pain bothersomeness, fear, worry, catastrophizing, depression) ⁵⁰	Free, evidence-based pain coping skills training programs (e.g. painTRAINER) and referral to local mental health providers who specialize in pain management
Physical Therapy	Persistent self-reported difficulty with walking or stair-climbing, balance difficulties, recent falls or pain as a limitation to engaging in regular exercise	Referrals based on patients' preferences for location, geography, and health insurance coverage
Weight Management & Nutrition Services	< 5% weight loss ⁵¹	Referrals to registered dieticians and other credentialled clinicians who specialize in weight loss support
Sleep Services	Sleep apnea: "high risk" based on the STOP questionnaire, score ≥ 2 ⁵² . Insomnia: score ≥ 11 on the Insomnia Severity Index ⁵³ .	Referrals for sleep testing, recommendations for free, evidence-based cognitive behavioral therapy for insomnia programs (e.g., CBTi-Coach app), and referrals to local providers or group programs focusing on sleep-related therapies.

Provider Intervention. As noted above, we have intentionally designed the PCP intervention to be brief, therefore maximizing feasibility and engagement. There are three components to the PCP intervention. The first is a set of brief videos summarizing current OA treatment guidelines, with a focus on practical application and the role of the PCP. Second, providers will receive progress reports for their enrolled patients through encrypted email or other UNC approved method of sharing PHI; this will include changes in symptoms and health behaviors from the study team at 6- and 12-months. Third, providers will be involved with referrals to additional clinical services, as described above. The OA CARE Navigator will provide the PCP with information on patient requests for referrals, based on the 6-month assessment, and the referral process will follow the usual procedures within the primary care clinic.

6.2 FIDELITY

Interventionist Training

OA Care Navigator: The OA Care will be trained by the principal investigator prior to delivering the intervention. This training will include general instruction in intervention delivery steps, processes for communicating with YMCA personnel and PCPs via email and the electronic health records, content for notes to PCPs, administration of 6-month screening questionnaires, and discussion of potential services and referrals during the 6-month phone call. For the 6-month screening questionnaires and discussion of referrals, training will

include mock sessions with both experienced study team members and non-study member volunteers (observed by the principal investigator). The *OA Care Navigator* will also view the video created for PCPs, as well as other materials from the OAAA, to become highly familiar with OA symptoms and care.

Fidelity Monitoring

Monitoring of Intervention Contacts. [name] or another experienced study team member will monitor study intervention contacts and provide feedback to the interventionists, including the following:

- *OA CARE* Navigator 6-month phone calls: The first 5 calls will be monitored with potential for additional calls if deemed appropriate by the principal investigator or other study team member. Monitoring will involve checks to ensure that all questions are asked per protocol, services and referrals are appropriately explained to patients, and the Navigator engages the patient in a meaningful discussion regarding their interest in services and referrals.

6.3 MEASURES TO MINIMIZE BIAS: RANDOMIZATION AND BLINDING

The randomization scheme will be generated by the study statistician and stored within the study database. The database will be configured so that blinded study personnel (e.g., those conducting follow-up assessments) will not have access to randomization information. The participants will not be notified of randomization assignment until all baseline assessments are complete. In addition, an individual participant's randomization assignment will not be known to any study personnel until baseline assessments are complete.

6.4 STUDY INTERVENTION ADHERENCE

The study database will be used to track participants' completion of all assessment visits, as well as all contacts with the *OA CARE* Navigator. The coordinator will also maintain close communication with the *OA CARE* Navigator regarding facilitation of all activities within the care pathway. The YMCA will provide documentation of patients' participation in specific YMCA programs to the *OA CARE* Navigator; this information will also be summarized for PCPs. Also, for each patient, the *OA CARE* Navigator will maintain a checklist of intervention activities, target dates, dates of completion, and comments.

